#### 9.1.12 ECG Procedure

Twelve-lead ECGs will be recorded using an ECG machine that automatically calculates the heart rate and measures PR interval, RR interval, QRS interval, QT interval, and QTcF. QTcF may also be calculated manually by the site.

All stationary 12-lead ECG machines will be supplied by the site. Subjects should be in a supine position and should have an approximate 10-minute rest period prior to ECG recordings. Should technical difficulties occur during recording of the ECG, a reasonable attempt should be made to repeat the ECG shortly after the failed attempt.

ECGs will be read automatically and the investigator or subinvestigator will also manually interpret the ECG using 1 of the following categories: within normal limits, abnormal but not clinically significant, or abnormal and clinically significant. All 12-lead ECGs will be stored for manual measurement of intervals, if necessary.

One copy of the 12-lead ECG with the physician's signature and date of assessment will be filed with the source documents and captured in the appropriate eCRF. If the original ECG is printed on thermal paper, the ECG report must be photocopied and certified. The photocopy will be filed with the original ECG in the source.

The schedule for ECG assessments in the SRD part of the study is shown in Appendix A and Appendix B and in the SRD/MRD part of the study is shown in Appendix C. When an ECG is scheduled at the same time as blood draws or vital signs, the blood draws and vital signs will take priority and the ECG will be obtained within 0.5 hours before or after the scheduled blood draw/vital sign assessment. If an ECG coincides with a meal, ECG will take precedence followed by the meal.

Additional unscheduled ECGs may be recorded where clinically necessary for subject safety. For eligibility determination, ECGs may be repeated once at Screening and/or Day -1.

## 9.1.13 Safety EEG Procedure

EEG data will be collected in a resting state with eyes open and closed, with photic stimulation, and with 3 minutes hyperventilation. EEG time may be adjusted in consultation with the PI and sponsor, and based on emerging PK or other data. When an EEG is scheduled at the same time as blood draws, the blood draws will take priority and the EEG will be obtained within 2 hours before or after the scheduled blood draw and/or vital sign assessment.

EEGs will be evaluated by a qualified individual for clinically significant abnormalities. Findings will be categorized as (1) within normal limits, (2) abnormal but not clinically significant, or (3) clinically significant abnormal. Abnormal EEG findings should be described. If a subject has a tremor during the study, an EEG must be conducted as soon as possible.

Prior to randomization, EEG reports must be reviewed by the investigator. Descriptive text reports will be provided for all screening and postdose EEGs. A subject with an EEG categorized as significantly abnormal during screening will not be eligible for randomization. To aid with EEG interpretation, video recordings and live streams of the volunteers' faces may be done during the EEG, at the investigator's and/or qualified individual's discretion.

A study manual of EEG assessments will be prepared and provided to the site before the start of the study. The EEG study manual will be stored with the study file.

Instructions for collecting, processing, and shipping of samples are provided in the laboratory manual.

# 9.1.15 Pharmacokinetic Sample Collection

9.1.15.1 Collection of Plasma and Urine for Pharmacokinetic Sampling

Blood and urine samples will be collected for the determination of concentrations of TAK-653, Urine samples will only be collected for the SRD/MRD Cohorts. The

sampling schedule may change based on emerging data but will not exceed the number of planned samples.

Serial blood and urine samples for determination of plasma and urinary concentrations of TAK-653 and its metabolites will be collected according to Table 9.c. The actual time of sample collection will be recorded on the source document and eCRF.

Table 9.c Collection of Blood and Urine Samples for Pharmacokinetic Analysis

Sample Type	Dosing Day	Time Postdose (hours)							
SRD (Cohorts	1-5)								
Plasma	1	Predose (within 15 minutes prior to dosing) and at 0.25, 0.5, 1, 1.5, 2, 3, 4, 6, 8, 10, 12, 16, 24, 36, 48, 72, 96, 120, and 144 hours postdose.							
SRD (Cohort 6	onward)								
Plasma	1	Predose (within 15 minutes prior to dosing) and at 0.25, 0.5, 1, 1.5, 2, 3, 4, 6, 8, 10, 12, 16, 24, 36, 48, 72, 96, 120, 144, and 168 hours postdose.							
SRD/MRD (Al	l cohorts)								
Plasma	1	Predose (within 15 minutes prior to dosing) and at 0.25, 0.5, 1, 1.5, 2, 3, 4, 6, 8, 10, 12, 16, 24, 36, 48, 72, 96, and 120 (a) hours postdose.							
Plasma	6	0.5, 1, 2, 4, 6, 8, 12, 16, and 24 (b) hours postdose.							
Plasma	12,14, 16	Predose (within 15 minutes of dosing) (and following collection procedure on Day 12, SRD/MRD Cohort 3 only).							
Plasma	18	Predose (within 15 minutes prior to dosing) and at 0.25, 0.5, 1, 1.5, 2, 3, 4, 6, 8, 10, 12, 16, and 24 hours postdose.							
Urine	1	Predose (-12 to 0 hours) and at (0 to 6), (6 to 12), (12 to 24), (24 to 48), and (48 to 72) hour intervals postdose.							
Urine	18	(0 to 6), (6 to 12), and (12 to 24) hour intervals postdose.							

a) The 120-hour sample must be collected before dosing on Day 6.

Blood samples (one 4-mL sample per scheduled time) for PK analysis will be collected into chilled Vacutainers containing anticoagulant (K2EDTA) according to the schedules in Appendix A, Appendix B, and Appendix C.

Blood samples for placebo will not be analyzed by the bioanalytical laboratory except for 2 samples per subject receiving placebo, 1 predose and the other around the expected time at which  $C_{max}$  occurred (as emerging from the actual measurement of the samples of the first dose group) to ensure from a safety perspective that no additional subjects could have been on active treatment.

Urine samples will not be collected for the SRD cohorts. Urine samples in the SRD/MRD for subjects randomized to placebo will not be analyzed.

Instructions for collecting, processing, and shipping of samples are provided in the laboratory manual.

b) The 24-hour sample must be collected before dosing on Day 7.

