#### **6.1.2** Part 2: SRD/MRD

Progression into the SRD/MRD Part 2 will occur only after review of all available safety, tolerability, PK, and PD data collected in at least the first 3 SRD cohorts. The actual dose in the SRD/MRD Cohorts will not be administered unless there is acceptable safety, tolerability, PK, and PD data at the same or higher dose level after a single dose in the SRD Cohorts. If necessary, the sponsor team (Takeda only) may unblind the data and perform additional analyses for an informed dose-escalation decision. The potential for accumulation and its impact on the likelihood of reaching the NOAEL exposure cap, will be taken into account when selecting doses for the MRD.

A single dose of TAK-653 or placebo will be administered on Day 1 followed by approximately 120 hours for safety, tolerability, PK, and PD assessments. Once daily (QD) multiple dosing will begin on Day 6 and continue through Day 18 (13 days). Initiation of the multiple-dose phase on Day 6 may be adjusted based on emerging safety, PK, and/or PD data. Neither sentinels nor

staggered dosing are used in the SRD/MRD. Subjects in the SRD/MRD Cohorts will be kept in the study unit for at least 72 hours after the last dose for safety assessments before discharge. The total confinement period planned is 21 days. Cohort 4 is optional, to be used if emerging safety and/or PK or PD data warrant further study at a different dose. Follow-up assessments will occur on Day 31 (±2).

Each dose cohort will be examined sequentially to ensure adequate evaluation of all available safety, tolerability, PK, and PD data prior to administering the next dose level.

The study schematic for the SRD/MRD Part 2 is presented in Figure 6.b. The schedule of assessments in the SRD/MRD Part 2 is in Appendix C.

Figure 6.b SRD/MRD Study Schematic

Pretreatr	nent Period		Tı	eatment Period			Follow- up (e)
Screening	Check-in Baseline Assessments	TAK-653 Single Dose Study Assessments (a) (b) (d)	Safety and PK Assessments (d)	TAK-653 QD dosing Study Assessments (a) (b) (c) (d)	Safety and PK Assessments	Study Exit	
Days -28 to -2	Day -1	Day 1	Days 2-5	Days 6-18	Days 19-20	Day 21	Day 31 (±2)
	4		Confin	ement			

- (a) Study assessments include PK sample collection throughout.
- (b)
- (c) For SRD/MRD Cohort 3 only, a single CSF sample will be collected from each subject on Day 12.
- (d)

A summary of the SRD/MRD dose cohorts is presented in Table 6.b.

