## 8.1.1.1 Sponsor-Supplied Drug

TAK-653 study drug will be supplied as 0.1, 0.25, 1, and 5 mg, and matching placebo as round, yellow-red film-coated tablets. TAK-653 drug product is manufactured by Takeda Pharmaceutical Company Ltd., Osaka, Japan.

TAK-653 tablets will be supplied in amber glass bottles with metal screw caps. Each bottle will contain 50 tablets.

Each bottle of TAK-653 active or placebo will bear a single-panel label that includes pertinent study information.

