- (q) Blood samples (4 mL) for PK analyses will be collected on Day 1 at predose (within 15 minutes prior to dosing) and at 0.25, 0.5, 1, 1.5, 2, 3, 4, 6, 8, 10, 12, 16, 24, 36, 48, 72, 96, and 120 hours postdose (the 120-hour collection should occur predose on Day 6). Blood samples for PK analyses will be collected on Day 6 at 0.5, 1, 2, 4, 6, 8, 12, 16, and 24 hours postdose (the 24-hour collection should occur predose on Day 7). Blood samples will be collected predose (within 15 minutes prior to dosing) on Days 12, 14, and 16. Blood samples will be collected on Day 18 predose (within 15 minutes prior to dosing) and at 0.25, 0.5, 1, 1.5, 2, 3, 4, 6, 8, 10, 12, 16, and 24 hours postdose. For Part 2 SRD/MRD Cohort 3 only, an additional PK blood sample will be collected following the collection procedure.
- (r) Urine samples for PK analyses will be collected on Day 1 predose at (-12 to 0 hours) and at (0 to 6), (6 to 12), (12 to 24), (24 to 48), and (48 to 72) hour intervals postdose. Urine samples for PK analyses will be collected on Day 18 at (0 to 6), (6 to 12), and (12 to 24) hour intervals postdose.
- (s) Study medication is dispensed QD on Day 1 and Days 6-18.
- (t) PTEs will be collected from signing of informed consent up until dosing on Day 1.
- (u) Any event after dosing on Day 1 will be captured as an AE.

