7.7 Pharmacokinetic/Pharmacodynamic Analysis

7.7.1 Plasma Pharmacokinetic Concentrations

Collection of Blood Samples for PK Analysis (All SRD Cohorts)

| Sample Type | Dosing Day | Scheduled Time (hours) |
|-------------|------------|---|
| Plasma | 1 | Predose (within 15 minutes prior to dosing) and at 0.25, 0.5, 1, 1.5, 2, 3, 4, 6, 8, 10, 12, 16, 24, 36, 48, 72, 96, 120 and 144 hours postdose. Additional collection at 168 hours postdose for Cohort 6 onward. |

Collection of Blood Samples for PK Analysis (All SRD/MRD Cohorts)

| Sample | | |
|--------|------------|---|
| Туре | Dosing Day | Scheduled Time (hours) |
| Plasma | 1 | Predose (within 15 minutes prior to dosing) and at 0.25, 0.5, 1, 1.5, 2, 3, 4, 6, 8, 10, 12, 16, 24, 36, 48, 72, 96 and 120 (a) hours postdose. |
| Plasma | 6 | 0.5, 1, 2, 4, 6, 8, 12, 16, and 24 (b) hours postdose. |
| Plasma | 12, 14, 16 | Predose (within 15 minutes prior to dosing) (and following ^{CCI} collection procedure on Day 12 (SRD/MRD Cohort 3 only). |
| Plasma | 18 | Predose (within 15 minutes prior to dosing) and at 0.25, 0.5, 1, 1.5, 2, 3, 4, 6, 8, 10, 12, 16, and 24 hours postdose. |

(a) The 120-hour sample must be collected before dosing on Day 6.

(b) The 24-hour sample must be collected before dosing on Day 7.

For each part, the concentration of TAK-653, ^{CCI} in plasma will be summarized by TAK-653 dose level, Day, and period (fasted vs fed) over each scheduled sampling time using descriptive statistics (N, arithmetic mean, SD, median, minimum, and maximum). Individual plasma concentration data versus time will be presented in a data listing.

| TAK-653-1001 | Page 19 of 32 |
|---------------------------------|----------------|
| Statistical Analysis Plan Final | 22 August 2017 |

Blood samples for placebo will not be analyzed by the bioanalytical laboratory except for 2 samples per subject receiving placebo, 1 predose and the other around the expected time at which C_{max} occurred (as emerging from the actual measurement of the samples of the first dose group) to ensure from a safety perspective that no additional subjects were on active treatment. These data will be listed but not summarized.

For each part, individual concentrations of TAK-653, ^{CCI} in plasma will be plotted by actual time on linear and semilogarithmic scales. Plots of mean TAK-653, ^{CCI} plasma concentrations versus nominal time will also be provided on linear and semilogarithmic scales.

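### The two-sample placebo assay names no study day and cannot check all 14 Part 2 doses or necessarily both food-effect periods; assaying plasma already drawn would cheaply widen the check

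*Protocol*

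**What the plan says.** Protocol 9.1.15.1 sends no placebo plasma for assay "except for 2 samples per subject receiving placebo, 1 predose and the other around the expected time" of Cmax. That time is to be taken "as emerging from the actual measurement of the samples of the first dose group". The purpose is "to ensure from a safety perspective that no additional subjects could have been on active treatment". SAP 7.7.1 repeats the rule and the purpose ("to ensure from a safety perspective that no additional subjects were on active treatment") and adds that the results are listed but not summarized. Neither text names a study day or sets a separate rule for Part 2 or for the food-effect cohort. Protocol 9.1.15.1 also leaves placebo urine unanalyzed.

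For Part 2, Appendix C states: "Study medication is dispensed QD on Day 1 and Days 6-18". Later plasma is already scheduled. Table 9.c has nine postdose samples on Day 6 and a predose sample plus 13 postdose samples on Day 18. Appendix C adds: "Blood samples will be collected predose (within 15 minutes prior to dosing) on Days 12, 14, and 16".

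On supply, Protocol 8.1.1.1 says: "Each bottle will contain 50 tablets". Two other controls exist. Protocol 8.6 has an unblinded person review the randomization schedule and dosing log around dosing. Protocol 9.2 requires observed dosing, mouth or hand checks and a recorded time for every dose.

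**The concern.** A rule that suits a single-dose subject is applied unchanged to a subject with 14 doses and to one dosed in two separate periods. A sample drawn before the first dose cannot show a dosing error. If the pair comes from Day 1, only one assay is informative, and only about the first dose. Supply in multi-tablet bottles suggests that each day's dose is made up separately, so a correct first dose does not by itself establish the later ones. With placebo urine unassayed, the 13 daily doses, or the fed period, could pass without any bioanalytical check.

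Safety is the primary objective, and SAP 7.1 pools placebo within each part. That gives 8 Part 2 placebo subjects on the protocol's four cohorts or 10 on the SAP's five. Active drug given unnoticed to a placebo subject on some days would put drug-related events into a small comparator group and leave an exposure unrecognised. In the food-effect cohort, SAP 7.9 reports placebo fed and placebo fasted separately, with two placebo subjects.

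**Working it through.** **The plan's own figures.** Part 2 doses: 1 (Day 1) + (18 − 6 + 1) = 14, matching the 14 treatment days in Protocol 2.0. Part 2 PK samples in Table 9.h: 13 + 2 + 3 + 9 + 1 + 2 + 1 + 1 + 13 + 1 = 46; 46 × 4 mL = 184 mL, as stated. One of the 46 is for SRD/MRD Cohort 3 only, so other cohorts have 45. Samples after the Day 6 dose: 9 + 3 + 14 = 26 (27 in Cohort 3). The rule assays 2 of 45 (4.4%).

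**Day 1 pair.** The predose sample covers no dose and the near-Cmax sample covers the Day 1 dose: 1/14 = 7.1%, whatever half-life or assay limit applies. If active drug were given on m of the 14 dosing days at random, the chance that Day 1 is among them is m/14:
- m = 1: 7.1%
- m = 2: 14.3%
- m = 7: 50%
- m = 14 (wrong arm throughout): 100%

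**Other sample sets.** A later sample can show an earlier dose through carry-over. The inputs are:
- Half-life: 10 h or 26 h (Protocol 4.1 and 6.2.1, predicted from rat and monkey).
- Peak at 2 h: assumed.
- Detection down to 10% or 1% of peak: assumed, as no assay limit is given.

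Detection window after the peak = t½ × log2(1/threshold). For 10 h this is 33 h (10%) or 66 h (1%); for 26 h it is 86 h or 173 h. A dose counts as covered if an assayed sample falls after it and within that window.

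| Samples assayed | Doses covered of 14, t½ 10 h | t½ 26 h |
|---|---|---|
| Day 1 pair | 1 | 1 |
| Day 18 pair (the wording allows it) | 2–3 | 4–8 |
| Best of any two scheduled samples | 3–5 | 7–13 |
| Day 1 pair + Day 18 near-Cmax | 3–4 | 5–9 |
| The same + Day 12, 16 and 18 predose | 5–8 | 10–14 |

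Each range runs from the 10% to the 1% threshold.

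**Sensitivity to human data.** Protocol 6.2.2 gives Day 18 means at 1 mg of 24.9 ng/mL (Cmax) and 503 h*ng/mL (AUC24). Cmax/Cav = 24.9/(503/24) = 1.19. In a one-compartment bolus model this implies a half-life of about 47 h, a rough upper figure. At 46 h a Day 18 pair covers 7–13 of 14, while a Day 1 pair still covers 1.

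**The log review.** Protocol 8.6 lists the MRD dosing days as 1 and 4 to 16. Protocol 6.1.2 and Appendix C give Days 1 and 6 to 18. Read literally, the review list omits Days 17 and 18 and includes Days 4 and 5, which have no dose. These passages must be reconciled.

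**The case against.** The strongest reply has four parts.

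- **The purpose is worded per subject, not per dose.** A placebo subject on the active arm throughout is found by a Day 1 pair with certainty. This stands. A reader might infer that the check fails its stated purpose; the documents do not support that. What it can miss is active drug on some days only.
- **Day 1 is nowhere stated.** This also stands. Taking the Cmax time from the first dose group points towards Day 1, but a Day 18 pair fits the wording, and its predose sample would be informative. The firm finding is that the day is open and that two samples fall short of 14 doses at the predicted half-lives.
- **Other controls act at each dose.** Observed dosing and the log review make an undetected mix-up less likely. They check procedure and records rather than what is in the plasma, and the review's day list conflicts with the dosing days.
- **The effect on the comparison is easily overstated.** A reader might infer that a missed error misclassifies 10% to 12.5% of the Part 2 placebo group (1/10 or 1/8). That size fits a subject on active drug throughout, which the check detects. An occasional wrong dose makes a partly exposed subject, and laboratory, vital-sign and ECG summaries carry no statistical tests.

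A longer human half-life would also help: at about 46 h with detection at 1% of peak, one Day 1 and one Day 18 near-Cmax sample would cover all 14 doses. That depends on taking a sample late, which the rule does not require.

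**Conclusion.** The point holds as a cheap improvement. The rule does not say which day is sampled and makes no allowance for repeated dosing or for the second food-effect period. On the likelier Day 1 reading it covers 1 of 14 Part 2 doses, a figure that needs no pharmacokinetic assumption. At the predicted half-lives no two scheduled samples cover all 14. The other coverage figures rest on an assumed 2 h peak, simple exponential decline and detection at 10% or 1% of peak. Nothing shows that a mix-up occurred or that any planned analysis is wrong.

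**What to change.** In Protocol 9.1.15.1 and SAP 7.7.1:

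- Name the sampling days, and keep the predose assay (the subject's own blank) and the Day 1 near-Cmax assay.
- For Part 2 placebo subjects, add at least one Day 18 near-Cmax assay, preferably with the Day 12, 16 and 18 predose samples. Predose samples alone would never cover the Day 18 dose.
- For food-effect placebo subjects, assay one near-Cmax sample in each period.
- Reconcile the MRD day list in Protocol 8.6 with Protocol 6.1.2 and Appendix C.

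The cost is one extra assay for each of 8 to 10 Part 2 placebo subjects (8–10), or four each (32–40), plus about 2 for the food-effect cohort: roughly 10 to 40 in all. No new blood is needed, assuming stored samples remain usable. Coverage improves but is not complete, except with the fuller set under the most favourable assumptions (26 h, 1%).

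If the sponsor prefers no extra assays, the stated purpose should be narrowed to detecting assignment errors at the sampled dose.

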## 9.1.15.3 Bioanalytical Methods

Plasma and urine concentrations of TAK-653 and concentrations of TAK-653 and in the concentration of the concentration of TAK-653 and in the concentrati

Part of the archival plasma and urine samples will be sent to Takeda Pharmaceutical Company Limited (Japan) for potential analysis of unknown metabolite characterization, if appropriate.

#### 9.1.16 Pharmacokinetic Parameters

The PK parameters of TAK-653, will be determined from the concentration-time profiles for all evaluable subjects. Actual sampling times, rather than scheduled sampling times, will be used in all computations involving sampling times. The following PK parameters will be calculated for plasma concentration values of TAK-653, in

Symbol/Term	Definition
Plasma	
AUC 24	Area under the plasma concentration-time curve from time 0 to 24 hours postdose.
$AUC_{\tau}$	Area under the plasma concentration-time curve during a dosing interval, where tau $(\tau)$ is the length of the dosing interval.
AUC last	Area under the plasma concentration-time curve from time 0 to time of the last quantifiable concentration.
$AUC_{\infty}$	Area under the plasma concentration-time curve from time 0 to infinity, calculated as $AUC_{\infty}=AUC_{last}+C_{last}/\lambda z$
CCI	
CCI	
$C_{av,ss}$	Average plasma concentration at steady state, calculated as $AUC_{\tau}/\tau$ .
C max	Maximum observed plasma concentration.
C max,ss	Maximum observed steady-state plasma concentration during a dosing interval.
CCI	
$\lambda_z$	Terminal disposition phase rate constant, calculated as the negative of the slope of the log-linear regression of the natural logarithm concentration-time curve during the terminal phase.
τ	Dosing interval.
C	
t max	Time of first occurrence of $C_{max}$ .
CCI	
CCI	
Urine	
CCI	

## 9.1.17 Pharmacodynamic Sample Collections

[figure not shown]

Table 9.e Collection of Blood Samples for Analysis

rt 3 onward)								
SRD (Cohort 6 onward) and SRD/MRD (Cohort 3 onward)								
Predose and 4, 8, 12 hours postdose								
24, 48, 72, 96 hours postdose								
Predose and 4, 8, and 12 hours postdose								
24 hours postdose								

Note: A single dose is administered on Day 1. No additional doses are administered until Day 6 when QD dosing begins from Day 6 through 18.

he subjects will be required to consent to this additional analysis.

# 9.1.18 Pharmacodynamic Parameters

9.1.18.1 CCI

## 9.1.19 Documentation of Screen Failure

Investigators must account for all subjects who sign informed consent. If the subject is found to be not eligible at this visit, the investigator should complete the eCRF screen failure form.

The primary reason for screen failure is recorded in the eCRF using the following categories:

- PTE/AE.
- Did not meet inclusion criteria or did meet exclusion criteria (specify reason).
- Significant protocol deviation.
- Lost to follow-up.
- Voluntary withdrawal (specify reason).
- Study termination.
- Other (specify reason).

Subject numbers assigned to subjects who fail screening should not be reused. If a subject fails screening, but is later successfully rescreened, the data for the subject will be entered as if these were 2 separate subjects. Therefore the data should be entered as follows:

- 1. The screen failure data should be entered as a screen failure subject.
- 2. Rescreened subjects should be assigned a new subject number and treated as a stand-alone subject.

